**Table 7. Protocol deviations**

| Deviation   |
|---|
| Any subject that conducts their 3 months after last treatment visit out of window by greater than 21 days or earlier than 7 days                            |
| Any subject not treated according to the assigned treatment.  |
| Any subject that does not have a Blinded Evaluator GCRS onsite live assessment at the primary endpoint visit (3 months after last treatment).               |
| Any subject that does not have an available Baseline (or screening if combined) Blinded Evaluator GCRS onsite live assessment.                              |
| Any subject that does not have grade 1 or 2 on either the Blinded Evaluator or Treating Investigator GCRS onsite live assessment at screening and Baseline. |

Galderma

Protocol number: 43USCH2208

Protocol V4.0

| Deviation  |
|--|
| Any subject with prohibited concomitant treatments/procedures prior to the 3 months after last treatment visit considered to have a substantial impact on the primary efficacy outcome.  |
| Any subject with a prohibited medical history, unstable medical history condition, or medical history condition that worsens prior to the 3 months after last treatment visit considered to have a substantial impact on the primary efficacy outcome. |

Protocol deviations will be presented descriptively. The number and percentage of subjects who have protocol deviations, the total number of deviations and the type of protocol deviation will be summarized using the ITT Population. The above summary of protocol deviations will be repeated by site as well. Protocol deviation listings will be reviewed, and each subject will be classified as belonging to the per-protocol set or not. Exclusions from the PP Population will be identified and documented prior to database lock.

Protocol deviations will be presented in a data listing that will display the visit where the deviation was reported, the date where the deviation occurred, the deviation type and description, the action taken, if it was reported to the Institutional Review Board (IRB) and if the deviation was due to COVID-19. Subjects who are excluded from the PP Population will also be presented in a data listing, along with their reason(s) for exclusion.

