## 8.5 Prior and Concomitant Medications

Prior medications are defined as medications that have been used within 30 days preceding the Screening visit or within the timelines specified in the Inclusion/Exclusion criteria, and then stopped prior to the Screening visit. Concomitant medications are any existing medications ongoing at the time of the Screening visit, any changes to existing medications during the study or any new medications received since the Screening visit. Subjects' prior medications will be collected at Screening and concomitant medications will be collected at all study visits.

Prior and concomitant medication summaries will be reported using the ITT Population in two different tables. The number and percentage of subjects reporting prior/concomitant medications and the number of events will be summarized by the WHO Drug Dictionary Anatomical Therapeutic Chemical 4th level (ATC-4) and the Preferred Term (PT). If the 4th level term is not available, the next available level (e.g., Anatomical Therapeutic Chemical 3rd level (ATC-3)) will be used. ATC-4 and PT will be presented by overall descending frequency first, then alphabetically if there are ties. Anatomical Therapeutic Chemical 4th level and PTs will be sorted in descending frequency first (by Restylane Lyft with Lidocaine group) and then alphabetically if there are ties. Each subject will only be counted once within each Anatomical Therapeutic Chemical (ATC) and ATC/PT combination. The subset of concomitant medication administered for treatment-related adverse events (see [Section 10.2.3](#)) will be summarized in the same way in an additional table.

All prior and concomitant medication data for each subject will be included in a data listing that will present the name of the medication, the ATC and PT, the indication, the total daily dose, the route, the start and end date, the reason of administration, and the related medical history and/or adverse event when it applies.

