**Table 8. Imputation Criteria for Missing/Partial Dates**

| Variable                            | Missing Day  | Missing Month or Day and Month   | Missing Year, Month and Year, or Day and Year   | Missing Day, Month, Year                        |
|-------------------------------------|--|--|---|---|
| Adverse Event/Medication Start Date | Assign to the first of the month (i.e., UNK-JAN-2023 becomes 01-JAN-2023)  | Assign to the month of ‘June’ (i.e., 01-UNK-2023 becomes 01-JUN-2023), provided the imputed date is on or after the subject’s Baseline study treatment date; otherwise, the subsequent month after study treatment will be used. | Assign to year of Baseline study treatment (i.e., 01-JAN-UNK becomes 01-JAN-2019), provided the imputed date is on or after the subject’s study treatment date; otherwise, the date of Baseline study treatment will be used. | Assign to Baseline study treatment date         |
| Adverse Event/Medication End Date   | Assign the last day of the month (i.e., UNK-JAN-2023 becomes 31-JAN-2023). | Assign to the subsequent month after the start date.   | Assign to the year of Baseline study treatment (i.e., 01-JAN-UNK becomes 01-JAN-2023), provided the imputed date is after the start date; otherwise, the subsequent year after start date will be used.                       | Assumed AE/medication is ongoing; no imputation |

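### SAP Table 8 pushes incomplete medication start dates to on or after the injection and can drag a pre-Screening stop along with them; the exposure is limited to the descriptive medication tables

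*SAP*

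**What the plan says.** SAP 11.2 says Table 8 governs any missing dates. The table has one start row and one end row, each shared by adverse events and medications.

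- **Start, month missing (or day and month):** June is used, "provided the imputed date is on or after the subject"'s Baseline treatment date; "otherwise, the subsequent month after study treatment will be used".
- **Start, year missing (alone or with day or month):** the Baseline year is used if that puts the date on or after treatment; "otherwise, the date of Baseline study treatment will be used".
- **Start, wholly missing:** "Assign to Baseline study treatment date".
- **End, month missing (or day and month):** "Assign to the subsequent month after the start date".
- **End, wholly missing:** "Assumed AE/medication is ongoing; no imputation".

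A start lacking only its day goes to the first of the recorded month, with no floor.

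SAP 8.5 defines prior medications as those used in a look-back period "and then stopped prior to the Screening visit". Anything ongoing at Screening, changed during the study or started since Screening is concomitant. Protocol 4.3.1 draws the same line.

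**The concern.** A floor at the first injection suits adverse events, because SAP 10.2 analyses only those occurring after treatment. It does not suit medications. A drug stopped before Screening, or already being taken then, cannot have started on or after the injection, yet three of the four start columns put it there. No rule keeps the imputed start from falling after a recorded stop.

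The stop row can carry the error forward. When the stop also lacks its month, it is built from the start that has just been moved, so a course that ended before Screening can reappear after the injection. At stake are the prior and concomitant counts in the SAP 8.5 tables and their agreement with the listings, which show dates as collected.

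**Working it through.** The plan states no figure to reproduce; the check applies Table 8 to partial dates. Injection and Screening dates below are assumed, since the documents give no enrolment dates. Where the day is also missing, day 1 is assumed.

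**1. The floor over a full year.** The month-missing start rule was applied to each of 365 injection dates in one year, with recorded start years equal to the injection year, one year earlier and five years earlier, and recorded days 1, 15 and 31.

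| Reading of the fallback | Recorded start year | Starts left before the injection |
|---|---|---|
| Literal: the calendar month after treatment | Same or earlier | 0 of 365 |
| Recorded year kept, month replaced | Earlier | 365 of 365 |
| Recorded year kept, month replaced | Same | 31 of 365 (December injections) |

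On the literal reading, an earlier-year start lands at most 31 days (day 1) to 61 days (day 31) after the injection. The year-missing and wholly missing columns end on or after the injection under either reading.

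**2. Recorded year overridden.** Injection 12-SEP-2023, start UNK-UNK-2019. June 2019 precedes the injection, so the literal fallback gives October 2023.

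**3. Start after a known stop.** Same injection, start UNK-UNK-2021, stop 20-AUG-2023. The start becomes 01-OCT-2023, after the stop. The stop is unchanged, so the drug remains prior under SAP 8.5; the record is impossible but not reclassified.

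**4. Stop carried past Screening.** Screening and injection in January 2024, start and stop both UNK-UNK-2023. June 2023 precedes the injection, so the start becomes February 2024 and the stop, one month after the start, becomes March 2024. The recorded stop year lies wholly before Screening, so the drug is prior by definition, yet it is counted as concomitant. This needs the literal reading of both cells; if the recorded year is kept, the course stays in 2023 and remains prior.

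**5. Position relative to Month 3.** Injection 15-JAN-2024, start UNK-UNK-2024. June is on or after the injection, so the start is 01-JUN-2024, which is day 16 + 29 + 31 + 30 + 31 + 1 = 138. Month 3 is 84 days after last treatment. Its latest in-window day after a touch-up is 28 + 7 + 84 + 14 = 133, so this start falls after Month 3. Over the year, 67 (day 1) to 96 (day 31) of 365 injection dates give a same-year start beyond day 84.

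**6. Where imputed medication dates are used.** SAP 8.5 plans counts by ATC level and preferred term, and no analysis of medication duration or timing. Per-Protocol exclusions come from a review of deviation listings before database lock (SAP 7). The sensitivity analysis that drops subjects with prohibited treatment identifies them by deviation type (SAP 9.1.3). The primary estimand uses the observed response after prohibited treatment (SAP 9.1.1).

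**The case against.** The strongest reply is that the class depends on the stop, not the start. A drug with a known pre-Screening stop stays prior, and one ongoing at Screening is concomitant whatever its start. That is correct, and it confines misclassification to records whose stop is itself rebuilt from the moved start. Such records are probably few. Under the 30-day look-back, a stop in the previous calendar year requires Screening by 30 January (30 January minus 30 days is 31 December), although the eligibility timelines may reach further back.

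Second, the fallback may mean only that the missing month is replaced and the recorded year kept. The wording does allow doubt. But keeping an earlier year would leave the date before treatment, which is the condition the fallback exists to avoid. Even on that reading, same-year starts still move past the injection except for December injections. Two programmers could code the cell differently, which is reason enough to settle it.

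Third, SAP 8.5 does not cite Section 11.2, whereas the adverse-event sections do. That is true, but the Table 8 row labels name medications explicitly.

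A reader might go further and infer that a washed-out prohibited drug would appear as used between injection and Month 3 and so remove the subject from the Per-Protocol set, since Table 7 lists "Any subject with prohibited concomitant treatments/procedures prior to the 3 months after last treatment visit" as a ground for exclusion. The documents do not support this. That ground also requires a judged substantial impact on the primary outcome, it rests on deviation review, and listings show the partial date as collected. Nor do they support a link to the restriction on certain medications in the 14 days before treatment: protocol 5.3.1 has prohibited medication checked before any treatment is given. Step 5 also shows that an imputed start need not fall before Month 3.

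**Conclusion.** The rule is wrong as written for medications, and the consequence is minor. Read literally, every medication start missing its month, its year or the whole date is placed on or after the injection, and nothing prevents a start later than a known stop. Reclassification from prior to concomitant is demonstrable where the recorded stop year is wholly before Screening and both months are missing, as in step 4, on the literal reading. In the other cases described, only the start date is wrong.

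The exposure is the descriptive prior and concomitant medication tables. No effect is shown on the primary analysis, Per-Protocol exclusions, the prohibited-treatment sensitivity analysis or the 14-day pre-injection check. The documents do not say how many medication dates are partial, so the number of affected records cannot be computed.

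**What to change.** Give medications their own start and stop rows in Table 8 and keep the Baseline-treatment floor for adverse events only. For medications:

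- Keep every recorded date part, including the year.
- Set the start to the earliest date compatible with the recorded parts, never after a recorded stop. A start with no recorded year is taken as before Screening.
- Set a partial stop to the latest date compatible with its own recorded parts, capped at last contact, and never derive it from an imputed start. A wholly missing stop can remain ongoing.
- Classify as prior only if the stop is before Screening. Where a partial stop could fall on either side of Screening, treat the drug as concomitant by convention.

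In step 4 this gives 01-JAN-2023 to 31-DEC-2023, which is prior. It does not resolve every record: with an injection on 12-SEP-2023 and start and stop both recorded only as 2023, the latest compatible stop is 31-DEC-2023 (or last contact, if earlier), so the drug stays concomitant even if it was really stopped before Screening. That is a stated conservative convention.

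The cost is two table rows and the matching derivation code, with no new data.

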**10.2 Adverse Events**

Adverse Event reporting on each subject will start once a subject is enrolled in the study. All other events that occur after the subject signs the ICF but before enrollment will be recorded in the subject's medical history. The reporting shall continue during each follow-up visit (including telephone contacts and extra visits between planned visits) until the last scheduled visit in the study.

All AEs reported will be listed, documenting the verbatim term, MedDRA Preferred Term (PT) and System Organ Class (SOC), affected area, event start and end date (or ongoing), seriousness (yes/no), intensity, relationship to study product (yes/no), relationship to injection procedure (yes/no), UADE status, AESI status, action taken, outcome, time to onset, duration and Injection Timepoint. All AE endpoints will be presented Overall. The Overall Summary of Adverse Events table and the Adverse Events by System Organ Class and Preferred Term table will be presented Overall and by Injection Timepoint in which they occurred (see definition in [Section 4.5.2](#)). Additional presentations of AE endpoints may be presented by Injection Timepoint on an as needed basis.

Only AEs occurring after treatment will be included in analysis. AEs occurring before initial treatment, if any, will only be presented in data listings. Missing dates, intensity, relationship, and seriousness will be imputed as described in [Section 11.1](#) and [Section 11.2](#).

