### 10.2.4 Time to Onset and Duration of AEs

Time to onset and duration of related AEs will be recorded. Time to onset of an AE will be derived as the AE start date minus the date of most recent prior treatment. If the AE start

Effective date: 2024-05-29 18:37

Effective

Version: 1.0

Galderma

Protocol number: 43USCH2208

Protocol V4.0

date is partially/completely missing, it will be imputed using the imputation rules specified in [Section 11.2](#).

Duration of an AE will be derived as the AE stop date minus the AE start date + 1. If the AE start date is partially/completely missing, it will be imputed using the imputation rules specified in [Section 11.2](#). A completely missing AE stop date will not be imputed and therefore no duration will be calculated in these cases.

The number of days to onset and the duration of each respective related AEs will be summarized by SOC and PT using the mean, SD, min, max and median. These summaries are at the event level so that subjects will be counted once for each multiple related AE they experience. Related AEs with onset >21 days after the most recent treatment will be listed.

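### SAP Table 8 can impute AE stop dates that are implausible or contradict the recorded parts, and these dates feed the duration summaries in SAP 10.2.4

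*SAP*

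**What the plan says.** The end-date row of SAP Table 8 (Section 11.2), which serves adverse events and medications, has four cases.

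- **Day missing:** the last day of the recorded month.
- **Month missing, or day and month missing:** "Assign to the subsequent month after the start date". No condition is attached.
- **Year missing, alone or with day or month:** the Baseline-treatment year is tried first and kept only if the resulting date is after the start; "otherwise, the subsequent year after start date will be used".
- **All parts missing:** no imputation.

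SAP 10.2 brings these dates into the AE analysis: "Missing dates, intensity, relationship, and seriousness will be imputed as described in" Sections 11.1 and 11.2. SAP 10.2.4 then defines the derived variable: "Duration of an AE will be derived as the AE stop date minus the AE start date + 1". The only stop dates it leaves out are the empty ones: "A completely missing AE stop date will not be imputed and therefore no duration will be calculated in these cases". Partly recorded stop dates therefore enter the table of related-AE durations, which gives mean, SD, minimum, maximum and median by SOC and PT, counted per event. SAP 11.2 keeps the listings on the dates as collected.

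**The concern.** An imputation rule for a partial date should return a date that agrees with the parts that were recorded and does not fall before onset. Table 8 does not always do this. In the year-missing case it goes from the Baseline year straight to the year after onset, so an onset year later than Baseline is never considered. It also asks for a date strictly after onset, so an event that stops on the day it starts fails the test. In the month-missing case it never looks at the onset month, and it does not say what happens when the next month belongs to another year. No upper limit is set in either case.

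The consequence is confined to a descriptive safety table. Protocol 5.3.3 expects common injection reactions to clear within two to four weeks. In a preferred term with few events, one imputed duration above a year would dominate the mean and the maximum and could make a short reaction look persistent.

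**Working it through.** **Inputs.** The rules come from SAP Table 8; duration = stop − start + 1 comes from SAP 10.2.4. I read the Table 8 fallback as start year + 1. Event dates below are illustrations.

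**The plan's own examples.** Day missing: UNK-JAN-2023 gives 31-JAN-2023, as printed. Year missing: 01-JAN-UNK gives 01-JAN-2023, as printed, but only with a Baseline in 2023 and a start before 01-Jan-2023. That start precedes Baseline, so the example does not illustrate an AE arising after treatment.

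**Year missing, onset after the Baseline year.** Baseline 2023, start 10-Jan-2024, stop 25-JAN-UNK.
- Candidate 25-Jan-2023 is not after the start, so the fallback gives 25-Jan-2025.
- Duration: (25-Jan-2025 − 10-Jan-2024) + 1 = 381 + 1 = 382 days.
- Onset-year date: (25-Jan-2024 − 10-Jan-2024) + 1 = 16 days.

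**Year missing, same-day stop.** Baseline 2023, start 15-Nov-2023, stop 15-NOV-UNK.
- Candidate 15-Nov-2023 equals the start and so is not after it; the fallback gives 15-Nov-2024.
- Duration: 366 + 1 = 367 days, where the same-day date gives 1.

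**Month missing, recorded day fits the onset month.** Start 05-Oct-2023, stop 12-UNK-2023.
- Rule: 12-Nov-2023, 38 + 1 = 39 days.
- Earliest fit: 12-Oct-2023, 7 + 1 = 8 days. 12 November and 12 December also fit the recorded parts.

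**Month missing, December onset.** Start 20-Dec-2023, stop 28-UNK-2023.
- If the year rolls over: 28-Jan-2024, 39 + 1 = 40 days, contradicting the recorded 2023.
- If the recorded year is kept: 28-Jan-2023, −326 + 1 = −325 days, before onset.
- The only date that fits is 28-Dec-2023: 8 + 1 = 9 days.

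The month rule can also return a date that does not exist: an October onset with recorded stop day 31 is sent to 31 November.

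**Where the rule works.**
- 16-Nov-2023 to 22-NOV-UNK, Baseline 2023: 7 days.
- 28-Dec-2023 to 04-JAN-UNK, Baseline 2023: the fallback gives 04-Jan-2024, 8 days.
- Month missing and recorded stop day earlier in the month than the start day: the next month is the earliest fit.

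**How often, under assumptions.** Take Baseline on each day from 01-Jul-2023 to 31-Dec-2023 and true durations of 1 to 28 days, and delete one date part.
- With the month deleted, the rule overstates about 54–55% of events, giving 30 to 59 days.
- With the year deleted, it overstates 5% of events with onset 0–7 days after initial treatment, 20% with onset on days 28–35, and 73% with onset spread evenly over 336 days. The overstated values run from 366 to 394 days.

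These shares are conditional on a date part being missing. They say nothing about how often that happens.

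**Effect on a summary.** Suppose 19 events average 10 days and a twentieth is the 382-day case: (19 × 10 + 382)/20 = 28.6 days. With the onset-year value: (19 × 10 + 16)/20 = 10.3 days. In a set of nine 6-day events and one of 372 days, the mean is 42.6 and the median stays at 6.

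**The case against.** - **Deliberate caution.** SAP 11.1 assigns the most severe value to missing intensity, relationship and seriousness, and Table 8 sends a missing stop day to the end of its month. A rule that leans towards longer events fits that pattern. This stands for part of the month-missing case: with several fitting months, earliest or latest is a choice. It does not cover a date that contradicts the recorded year or precedes onset, or a one-day event counted as 367 days. Nor does it explain why a fitting same-year stop is accepted for onset in the Baseline year and skipped for a later onset.
- **A softer reading.** The fallback could mean the first year in which the recorded day and month fall after onset. That would remove most of the year-missing cases, though not the same-day stop. The text does not say this, and the month-missing case would be unchanged.
- **Rarity.** AE dates go into an eCRF with checks for incomplete data and a query process (Protocol 10.4.2), so such records may be uncommon. The documents give no count.

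A reader might draw three stronger conclusions that the documents do not support.

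- *Every partial stop date is imputed wrongly.* The cases where the rule works show otherwise, and even where the onset month or year fits, a later true stop is possible.
- *A stop after the last scheduled visit is impossible.* Protocol 7.9.7.1 follows related events past study end until they resolve, become chronic or stable, or the subject is lost to follow-up.
- *The comparison between arms is biased.* Duration is only described, the same rule serves both arms, and nothing shows an imbalance in partial dates. Diary symptoms are also reported separately from other AEs (Protocol synopsis, Safety Assessments).

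**Conclusion.** The point holds as a minor defect in a date rule. Where the year is missing, Table 8 can produce durations of roughly 366 to 394 days for short events, if onset falls in a calendar year after Baseline or the event stops on the day it starts. Where the month is missing, it passes over an onset month that fits, and for a December onset with a recorded stop year it gives a date that contradicts that year or precedes onset. The year-missing result for later onsets rests on the literal reading of the fallback; the same-day and December results do not.

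The size in the trial cannot be stated, because the number of partial stop dates is unknown. Means and maxima of related-AE duration by SOC and PT are exposed. Medians are little affected, and the listings and the primary endpoint are not affected.

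**What to change.** Reword the end-date row of SAP Table 8:

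1. **Year missing:** use the first year in which the recorded parts give a date on or after the start date. The onset year is then tried first, and a stop equal to the start is allowed.
2. **Month missing:** use a month that is consistent with the recorded day and year and not before the start. Take the onset month if it fits and otherwise the next that does; or, if the sponsor wants a conservative rule, take the latest fitting month and say so.
3. **Day also missing:** use the last day of the imputed month, as the table already does when only the day is missing.
4. **Upper limit:** cap the imputed stop at the subject's last recorded contact, including AE follow-up after the study, rather than at the last scheduled visit.

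The cost is a few sentences in Table 8 and a small program change, with no new data. The downside is that an earliest-fit rule may understate the duration of some events, so the chosen direction should be stated with the table.
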